9. SAFETY EVALUATION

All summaries and analysis of safety data will be presented for the Safety Analysis Population. Safety summaries will be presented overall and grouped by study arm.

Continuous variables will be summarized using the following descriptive statistics: n (non-missing sample size), mean, standard deviation, median, maximum and minimum. All categorical measures will be summarized by the frequency and percentages of observed levels will be reported for all categorical measures. The denominator for the percentages may be based on the number of non-missing observations for an assessment or based on the number of subjects in a population. This will be described for each table.

9.1. Demographic and Other Baseline Characteristics

Summaries of age, sex, ethnicity, race, BMI, and prior receipt of seasonal influenza vaccine will be presented by site ([Table 16](#), [Table 17](#)) and by study arm ([Table 18](#), [Table 19](#)). Age will be summarized as a continuous variable. Ethnicity is categorized as Hispanic or Latino, or not Hispanic and not Latino. In accordance with NIH reporting policy, subjects may self-designate as belonging to more than one race or may refuse to identify a race, the latter reflected in the electronic case report form (eCRF) as “No” to each racial option. BMI will be summarized as a continuous as well as categorical variable, categorized as (<30, ≥30). Self-reported history of prior receipt of seasonal influenza vaccine will be categorized as follows: Either 2017-2018 or 2018-2019, Neither 2017-2018 or 2018-2019, or unknown. Demographic information for individual subjects will be provided in [Listing 6](#). Subjects’ prior influenza vaccination history (seasonal and non-seasonal) will be provided in [Listing 8](#).

9.1.1. Prior and Concurrent Medical Conditions

All current illnesses and past or pre-existing medical conditions will be coded using Medical Dictionary for Regulatory Activities (MedDRA®) version 20.0 or higher.

Summaries of subjects’ prior and concurrent medical conditions will be presented by study arm ([Table 20](#)).

Individual subject listings will be presented for all reported medical history including prior and concurrent medical conditions ([Listing 7](#)).

9.1.2. Prior and Concomitant Medications

Concomitant medications will be coded to the Anatomical Therapeutic Classification using the WHO Drug Dictionary. The use of concomitant medications during the study will be summarized by ATC1 and ATC2 code and study arm for the Safety Population ([Table 169](#)). A listing of concomitant medications will be presented ([Listing 27](#)).

9.2. Measurements of Treatment Compliance

All subjects are to receive 2 study vaccinations administered in the clinic. The number of subjects receiving study vaccination by month will be presented by study arm and by site in [Table 14](#) and [Table 15](#) and as part of the subject disposition table ([Table 13](#)). [Listing 1](#) presents subjects who received investigational product with randomized study arm and study product received for each study vaccination.

9.3. Adverse Events

A summary of all adverse events is provided in [Table 117](#). A summary of those events that occurred in $\geq 5\%$ of subjects in any study arm is provided in [Table 118](#).

9.3.1. Solicited Events and Symptoms

Systemic solicited adverse events were collected pre-vaccination, and systemic and local solicited adverse events were collected at-least 20 minutes post-vaccination and then daily for 7 days after the first study vaccination and graded on a scale of 0 (none), 1 (mild), 2 (moderate) and 3 (severe). Systemic events include fever, feverishness, fatigue, malaise, myalgia, arthralgia, headache, and nausea. Local events include pruritus, ecchymosis, erythema, induration/swelling, pain, and tenderness. Ecchymosis, erythema, and induration are measured by both functional and measurement grading scales as defined in [Table 7](#). The grading scale for systemic events, including quantitative grading for fever, is included in [Table 8](#).

When calculating the incidence of solicited events, each subject will be counted once at the highest severity following the applicable vaccination, and any repetitions will be ignored. For summaries presented for the first study vaccination, the denominator for percentages will be the number of subjects who received the first study vaccination with non-missing data for the event summarized.

The number and percentage of subjects reporting at least one solicited adverse event of each severity will be summarized for each solicited symptom, any systemic symptom, any local symptom, and any symptoms. For each event the denominator is the number of subjects who received the first study vaccination with non-missing data for the specific event. The 95% CI calculated using Clopper-Pearson methodology from a binomial distribution (SAS Proc Freq with a binomial option) will be presented ([Table 119](#)). Logistic regression models will be fit to estimate the effect of study arm on the probability of reporting any local event or reporting any systemic event ([Table 120](#), [Table 121](#)). If statistically significant effects are observed in the model for local events or systemic events, then additional models may be fit for each individual event of that type.

$$\text{logit}[P(\text{Event})] = \beta_0 + \beta_1 \times \text{Treatment} + \varepsilon,$$

For each systemic and local event, any systemic event, any local event, and any solicited event, the maximum severity over 7 days after the first study vaccination will be summarized for the Safety Population. The number and percentage of subjects reporting each event will be summarized by the maximum severity and study arm. For each event the denominator is the number of subjects who received the first study vaccination with non-missing data for the specific event. The 95% CI calculated using Clopper-Pearson methodology from a binomial distribution (SAS Proc Freq with a binomial option) will be presented ([Table 122](#)).

The number of subjects reporting a solicited adverse event will be summarized for each day post the first study vaccination combined both in a summary table ([Table 123](#)) and graphically in a bar chart ([Figure 96](#) and [Figure 97](#)).

Systemic and Local solicited events reported by subject will be presented in [Listing 20](#) and [Listing 21](#), sorted by subject ID, vaccination number, parameter, and study day.

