### 5.1.2 Subject Exclusion Criteria

Subjects eligible to participate in this trial must not meet any of the following exclusion criteria:

1. Have an acute illness, as determined by the site PI or appropriate sub-investigator, within 72 hours prior to study vaccination.

*An acute illness which is nearly resolved with only minor residual symptoms remaining is allowable if, in the opinion of the site PI or appropriate sub-investigator, the residual symptoms will not interfere with the ability to assess safety parameters as required by the protocol.*

2. Have any medical disease or condition that, in the opinion of the site PI or appropriate sub-investigator, is a contraindication to study participation.

*Including acute, subacute, intermittent or chronic medical disease or condition that would place the subject at an unacceptable risk of injury, render the subject unable to meet the requirements of the protocol, or may interfere with the evaluation of responses or the subject's successful completion of this trial.*

3. Have immunosuppression as a result of an underlying illness or treatment, a recent history or current use of immunosuppressive or immunomodulating disease therapy.
4. Use of anticancer chemotherapy or radiation therapy (cytotoxic) within 3 years prior to study vaccination.
5. Have known active or recently active (12 months) neoplastic disease or a history of any hematologic malignancy. Non-melanoma, treated, skin cancers are permitted.
6. Have known human immunodeficiency virus (HIV), hepatitis B or hepatitis C infection.
7. Have known hypersensitivity or allergy to eggs, egg or chicken protein, squalene-based adjuvants, or other components of the study vaccine.
8. Have a history of severe reactions following previous immunization with licensed or unlicensed influenza vaccines.
9. Have a history of GBS.
10. Have a history of convulsions or encephalomyelitis within 90 days prior to study vaccination.
11. Have a history of PIMMCs.

Refer to [Appendix B](#): Adverse Events of Special Interest

12. Have a history of alcohol or drug abuse within 5 years prior to study vaccination.
13. Have any diagnosis, current or past, of schizophrenia, bipolar disease or other psychiatric diagnosis that may interfere with subject compliance or safety evaluations.

As determined by the site PI or appropriate sub-investigator.

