Reactogenicity assessments will include an assessment of solicited AEs occurring from the time of first study vaccination through Day 8, which includes an assessment of injection site reactions including pruritus, ecchymosis, erythema, induration, edema, pain, and tenderness as well as systemic reactions including fever, feverishness, fatigue, malaise, myalgia (exclusive of the

injection site), arthralgia, headache, and nausea. Pre-administration reactogenicity assessments will be performed immediately prior to first study vaccination to establish baseline, then the study vaccination will be given.

Subjects will be observed in the clinic for at least 20 minutes after the first study vaccination only (administered during visit 1). Following the first study vaccination, the vaccination site will be examined, post-administration reactogenicity assessments will be performed, and any AE/SAEs will be recorded on the appropriate DCF prior to discharge from the clinic. The study vaccination site will also be examined on approximately Day 2 and Day 8.

All subjects will complete a Memory Aid from the time of first study vaccination through Day 8. Memory Aids will be reviewed with the subjects for any AEs (solicited injection site and systemic reactions as well as unsolicited AEs), SAEs and concomitant medications (including solicitation for receipt of any non-study influenza vaccines) at clinic study visits on approximately Day 2 and Day 8.

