### **7.2.1 Clinical Laboratory Evaluations**

Urine or serum pregnancy tests will be performed locally by the site at the screening visit (optional) and within 24 hours prior to first study vaccination for all women of childbearing potential. Results must be negative and known prior to randomization on Day 1 and administration of first study vaccination to be eligible for participation in this trial and receipt of study vaccination.

The ESR evaluation will be performed locally by the site at the screening visit and confirmed as less than 30 mm per hour to be eligible for participation in this trial and receipt of the first study vaccination.

Clinical safety laboratory parameters (WBC, Hgb, PLT, ALT, AST, GGT, ALP, Bilirubin (total), serum lipase and serum amylase and Cr) will be collected at the screening study visit and will be sent to the Central Clinical Laboratory. The results from the clinical safety laboratory parameters collected at the screening visit must be reviewed prior to the first study vaccination and must be

within acceptable ranges to be eligible for receipt of the first study vaccination (see [Section 5.1.1](#)). The safety laboratories will be repeated prior to receipt of the first study vaccination. However, the results from the clinical safety laboratory parameters collected prior to the study vaccination will not be available or reviewed prior to the study vaccination. Clinical safety laboratory parameters collected immediately prior to the first study vaccination will serve as the baseline and will be repeated on approximately Day 8.

The volume of venous blood to be collected for ESR and clinical safety laboratory evaluations is presented in [Table 3](#).

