### **9.2 Methods and Timing for Assessing, Recording and Analyzing Safety Parameters**

#### **9.2.1 Adverse Events**

**Adverse Event (AE):** ICH E6 GCP defines an AE as any untoward medical occurrence in a patient or clinical investigation subject administered a pharmaceutical product regardless of its causal relationship to the study treatment. The FDA defines an AE as any untoward medical occurrence associated with the use of a drug in humans, whether or not considered drug related.

An AE can therefore be any unfavorable and unintended sign (including an abnormal laboratory finding), symptom or disease temporally associated with the use of a medicinal (investigational) product. The occurrence of an AE may come to the attention of study personnel during study visits and interviews of a study recipient presenting for medical care, or upon review by a study monitor.

AEs, including solicited injection site and systemic (subjective and quantitative) reactions, not meeting the protocol-defined criteria for SAEs, will be recorded on the appropriate DCF and entered into the eCRF. Information to be collected for unsolicited non-serious AEs includes event description, date of onset, licensed study physician's assessment of severity and relationship to study product or alternate etiology (if not related to study product) (assessed only by those with the training and authority to make a diagnosis and listed on the Form FDA 1572 as the site PI or sub-investigator), date of resolution, seriousness, and outcome. AEs occurring during the trial-collection and reporting period will be documented appropriately regardless of relationship to study product. AEs will be followed through resolution.

Any medical condition that is present at the time that the subject is screened will be considered as baseline and not reported as an AE. However, if the severity of any pre-existing medical condition increases, it will be recorded as an AE.

AEs must be assessed for severity and relationship to study product (see definitions below). AEs characterized as intermittent require documentation of onset and duration of each episode. The start and stop date of each reported AE will be recorded on the appropriate DCF and entered into the eCRF.

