9.6. Clinical Laboratory Evaluations

Clinical safety laboratory parameters (WBC, Hgb, PLT, ALT, AST, T. Bili, GGT, ALP, Amylase, Lipase, Cr) will be collected from each subject prior to the first study vaccination and approximately 7 days the first study vaccination. These evaluations will be performed by the central clinical laboratory. The grading scale for clinical laboratory evaluations is presented in [Table 10](#). Clinical laboratory evaluations assessed on Day 1 prior to the first study vaccination will be considered as baseline.

The distribution of laboratory results by severity, study day and study arm will be presented starting with [Table 139](#) and ending with [Table 150](#). Descriptive statistics including mean, standard deviation, median, minimum and maximum values and change from baseline by study day will be summarized for each parameter starting with [Table 151](#) and ending with [Table 161](#). Box plots illustrating the change from baseline for each laboratory parameter will be presented starting with [Figure 102](#) and ending with [Figure 112](#). Subject visits with abnormal laboratory results, Grade 1 severity or higher, will be presented in [Table 162](#) and [Table 163](#) for Chemistry and Hematology parameters, respectively.

A complete listing of individual clinical laboratory results will be presented in [Listing 23](#) and [Listing 24](#) for chemistry and hematology, respectively, sorted by subject ID, parameter, and visit number.

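### Solicited systemic counts ignore the Day 1 pre-dose grade, and no planned table counts subjects whose symptom or laboratory grade worsened from Day 1

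*SAP*

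**What the plan says.** **Baseline.** Protocol 7.1 states: "Pre-administration reactogenicity assessments will be performed immediately prior to first study vaccination to establish baseline". SAP 9.3.1 narrows this: "Systemic solicited adverse events were collected pre-vaccination", while local symptoms are described as collected only from after the dose. For laboratories, Protocol 7.2.1 and SAP 9.6 make the Day 1 pre-dose sample the baseline. Entry is decided on the screening sample, taken up to 28 days before, and Protocol 7.2.1 adds that "the results from the clinical safety laboratory parameters collected prior to the study vaccination will not be available or reviewed prior to the study vaccination".

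**Solicited counts.** For incidence, SAP 9.3.1 says "each subject will be counted once at the highest severity following the applicable vaccination, and any repetitions will be ignored". For the severity summary, "the maximum severity over 7 days after the first study vaccination will be summarized for the Safety Population". Protocol 11.6.2 has the same rule: take the worst post-dose grade and split it into no symptom against any grade. The logistic model in SAP 9.3.1 has a treatment term only.

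**Laboratory counts.** SAP 9.6 says "The distribution of laboratory results by severity, study day and study arm will be presented starting with" Table 139 and ending with Table 150; those shells have a Baseline row and a Day 8 row for each arm. Tables 151-161 and Figures 102-112 summarise change from baseline in the measured value. Tables 162-163 list graded results by subject. Table 117 has a row for subjects with at least one abnormal clinical safety laboratory adverse event, with no statement of how it relates to Day 1.

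**The concern.** Reactogenicity and laboratory adverse events following the first vaccination are primary safety outcomes. A count meant to describe what followed vaccination should be readable against what was there before it. Here the pre-dose grade is collected for that purpose and then left out of the per-subject counts.

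Pre-dose symptoms are foreseeable. Footnote 4 to the exclusion criteria in Protocol 5.1.2 says "An acute illness which is nearly resolved with only minor residual symptoms remaining is allowable", subject to the investigator's judgement that the symptoms will not interfere with safety assessment. Graded Day 1 laboratory values are also foreseeable, because for several parameters Grade 1 starts right at the eligibility limit. A woman is eligible with creatinine below 1.1 mg/dL, and 1.1 is Grade 1. Lipase of 60 is eligible, and 61 is Grade 1.

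At stake are the absolute rates reported for each arm, and to a lesser degree the contrast between adjuvanted and unadjuvanted arms. By the asterisk convention of SAP 6.2.1, Tables 117 and 122 go into the Expedited Report, but Table 123, which holds the pre-dose column, does not.

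**Working it through.** The plan states no figure on this point, so there is none to reproduce. The check is of the counting rules, followed by an illustration of size.

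**Step 1: what each output does with the pre-dose grade.**

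- Table 117 (systemic rows), Tables 119 and 122 (systemic and any-symptom rows): highest post-dose grade, pre-dose grade not used.
- Table 121 (model for any systemic event): same event definition, treatment as the only term. A significant result may lead to symptom-level models.
- Table 123: has a Pre-Vac column by symptom, severity and arm, but does not cross it with the post-dose grade.
- Tables 139-150: Baseline and Day 8 as separate rows.
- Tables 151-161: change in value, not change in grade.
- Table 120 (local events): not affected, since SAP 9.3.1 describes no local pre-dose grade.

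**Step 2: why separate distributions are not enough.** Suppose 4 of 40 subjects in an arm are Grade 1 at baseline and 4 of 40 are Grade 1 at Day 8. If they are the same four people, nobody newly became abnormal. If they are eight different people, four did. The same two rows fit any number from 0 to 4, whatever the true prevalence. Change in value does not settle it either: a mean, SD, median and range do not count the subjects who crossed a grade boundary.

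**Step 3: size for solicited events.** Let *b* be the proportion with a pre-dose symptom that persists after dosing (assumed; equal across arms in expectation) and *q* the new-onset rate among the rest.

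Counted rate = *b* + (1 - *b*) × *q*

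For *q*, take 20% and 35%. These are the ends of the headache range in Protocol 2.3.1 for the earlier Advax-CpG formulation. They are used only as plausible values, not as control and adjuvant rates. With *b* = 2%: 0.02 + 0.98 × 0.20 = 0.216 and 0.02 + 0.98 × 0.35 = 0.363.

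| *b* (assumed) | Counted rates | Difference | Odds ratio | Extra subjects counted per 40 |
|---|---|---|---|---|
| 0 | 20.0% vs 35.0% | 15.0 points | 2.15 | 0 |
| 2% | 21.6% vs 36.3% | 14.7 points | 2.07 | 0.6 and 0.5 |
| 5% | 24.0% vs 38.3% | 14.3 points | 1.96 | 1.6 and 1.3 |
| 10% | 28.0% vs 41.5% | 13.5 points | 1.82 | 3.2 and 2.6 |

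The difference shrinks by the factor (1 - *b*): 15 × 0.98 = 14.7 and 15 × 0.90 = 13.5.

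**Step 4: scale against sampling error.** With 40 per arm, the 95% half-width for 20% against 35% is 1.96 × √(0.20 × 0.80/40 + 0.35 × 0.65/40) = 1.96 × 0.098, about 19 points. The dilution of 0.3 to 1.5 points is small beside that.

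**The case against.** The best defence is that the SAP follows Protocol 11.6.2, that counting every post-dose occurrence is the cautious choice for an adjuvant formulation not previously given to humans, and that the pre-dose data are not hidden. They appear in Table 123, in the Baseline rows of Tables 139-150, in the change summaries and in the listings. Comparisons are descriptive and randomised, and entry screening limits carry-over. For example, oral temperature must be below 100.0°F while Grade 1 fever starts at 100.4°F, so no eligible subject has graded fever at baseline.

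Most of this stands, and it is why the planned counts should stay. It does not supply the missing number: how many subjects got worse after the dose. That could be pieced together from listings, but no planned table gives it.

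Several stronger readings are tempting and should be resisted.

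- **That laboratory baselines are ignored, or that a Grade 1 value on both days is counted as an event.** Baseline is displayed and change in value is summarised. Whether such a subject enters the Table 117 row is undefined, not settled either way.
- **That the SAP breaks Protocol 9.2.1.** That section says "However, if the severity of any pre-existing medical condition increases, it will be recorded as an AE", but the rule concerns conditions present at screening. Screening laboratories must be in range, so the rule does not reach a new Day 1 abnormality. Solicited events have their own rule in 11.6.2.
- **That 10-28% of subjects are wrongly counted for laboratories.** Assuming a 1-3% chance per parameter gives 1 - 0.99^11 = 10.5% to 1 - 0.97^11 = 28.5% with at least one of 11 abnormal. That is an assumed Day 1 prevalence, not persistence to Day 8. It also assumes independence, which is doubtful for related tests such as ALT, AST and GGT.

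**Conclusion.** The point holds in a limited form. Solicited systemic counts include symptoms already present before dosing and unchanged afterwards. No planned table counts subjects whose symptom or laboratory grade rose from Day 1, and the Table 117 laboratory row has no stated relation to Day 1.

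A reader might infer bias for or against an adjuvant; randomisation means none is expected. Under the assumed 2-10% persistence, counted rates rise by 1.3 to 8.0 points per arm and a 15-point contrast loses 0.3 to 1.5 points. The persistence is an assumption because the documents give no pre-dose prevalence. It could be higher for the any-systemic row, which pools eight symptoms. The gap in the laboratory tables needs no such assumption. It is a reporting weakness worth correcting, and it does not invalidate the planned safety analysis.

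**What to change.** 1. **SAP 9.3.1.** Keep the all-occurrence counts of Protocol 11.6.2 as planned. Beside Tables 119 and 122, add counts of systemic events that are new onset or higher in grade than the same symptom's Day 1 pre-dose grade. Rerun Table 121 on that definition as a sensitivity analysis.
2. **SAP 9.6.** For each laboratory parameter, add a Day 1 by Day 8 grade shift table by arm, with a missing category.
3. **Table 117.** Define the laboratory adverse event row as a Day 8 grade above the Day 1 grade.
4. Leave local events and Table 120 unchanged.

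The cost is SAP text, programming and a few more tables; no new data are needed. Because the all-occurrence counts remain, the solicited-event rule in Protocol 11.6.2 is still followed. The one analytic drawback is that a symptom that resolves and then recurs at its pre-dose grade is missed by the added counts. It stays visible in the planned ones.
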